Study Title “The Efficacy Of Intravenous Immunoglobulin Therapy
In Treatment Induced Neuropathy Of Diabetes”

NCT number: NCT02915263

Version 2.0

Document Date: Revised 11/10/2016 (Original 9/10/2016)

Protocol:

This study will be a double-blind, placebo-controlled pilot study of the effects of immune globulin (IVIG) on treatment induced neuropathy in diabetes. The goal of this pilot study is to obtain preliminary data on the magnitude of the treatment effect of IVIG on the neuropathic pain and neuropathy severity associated with TIND. The preliminary data will be used to power a larger treatment trial, and to aid our understanding of the mitigating factors in the treatment response.

The study will include a total 20 individuals. Subjects will be randomized equally to treatment or placebo. Treatment will consist of IVIG administered at 2 grams/kg divided over 2-4 days, with a follow up treatment 3 weeks (+/-3 days) later of IVIG 1gram/kg administered over 1 day.

Subjects: All individuals participating in the study will be recruited from Joslin Diabetes Center or Beth Israel Deaconess Medical Center from the clinical practice of [name]. Recruited subjects will review and sign the informed consent, undergo screening for eligibility:

Inclusion Criteria:

- Individuals with a diagnosis of diabetes and treatment induced neuropathy (defined by the onset of neuropathic pain within 8 weeks of a change in HbA1C exceeding 3 points over 3 months).
- Ages 18-60.
-

Exclusion Criteria:

- No other known cause of neuropathy (chemotherapy, toxins, other medical disorder).
- Anticoagulation with warfarin, aspirin & Plavix together, or other anticoagulant that would place subjects at undue risk of bleeding from a skin biopsy. Aspirin or Plavix alone are not an exclusion criteria.
- Evidence of severe vascular disease (history of ulceration, poor wound healing, vascular claudication)
- Clinically active coronary artery or cerebrovascular disease
- History of allergic reaction to local anesthesia for skin biopsies or history of scarring or keloid formation.
- History of reaction to blood products or immune globulin.

Screening Visit (Visit 1): Protocol Procedures- After signing an informed consent subjects will undergo the following:

- 1) Undergo a general physical examination, Pain VAS scores, pain questionnaires and SF-36.
- 2) Have a quantified neurological (neuropathy) examination using the Utah Early Neuropathy Score (UENS)(Singleton *et al.*, 2008).
- 3) Undergo autonomic testing (heart rate variability to paced breathing)(Gibbons and Freeman, 2004). Heart rate variability is measured over the course of 6 deep inspirations with the peak maximal average heart rates subtracted from the lowest heart rates during each breathing cycle.
- 4) Undergo a 3mm punch skin biopsy at the distal leg to investigate small sensory and autonomic innervation using standard methodology (Gibbons *et al.*, 2009, Wang and Gibbons, 2013). Outcome measures will include intra-epidermal nerve fiber density (IENFD).
- 5) Quantitative review of additional clinical outpatient data (renal function, retinopathy screening, laboratory studies).

(Visit 2) Outpatient treatment 1: IVIG 2 grams/kg over 2-5 days (to be administered within 28 days of screening visit).

SF-36 questionnaire.

Placebo would include administration of 0.1% albumin per day over 2-5 days.

(Visit 3) Outpatient treatment 2: IVIG 1 gram/kg over 1 day (to be administered 21±3 days after completion of initial treatment).

SF-36 Questionnaire.

Placebo would include administration of 0.1% albumin per day over 1 day.

Visit 4: Follow up evaluation at BIDMC 28 +/- 3 days after 2nd IVIG treatment where they will undergo the following:

- 1) Undergo a general physical examination. Pain VAS scores, pain questionnaires and SF-36.
- 2) Have a quantified neurological (neuropathy) examination using the Utah Early Neuropathy Score (UENS)(Singleton *et al.*, 2008).
- 3) Undergo autonomic testing (heart rate variability to paced breathing)(Gibbons and Freeman, 2004). Heart rate variability is measured over the course of 6 deep inspirations with the peak maximal average heart rates subtracted from the lowest heart rates during each breathing cycle.
- 4) Undergo a 3mm punch skin biopsy at the distal leg to investigate small sensory and autonomic innervation using standard methodology (Gibbons *et al.*, 2009, Wang and Gibbons, 2013). Outcome measures will include intra-epidermal nerve fiber density (IENFD).
- 5) Quantitative review of additional clinical outpatient data (renal function, retinopathy screening, laboratory studies).

DOSING REGIMEN (Describe the subject or animal dosing)

(Visit 2) Outpatient treatment 1: IVIG 2 grams/kg over 2-5 days (to be administered within 28 days of screening visit).

Placebo would include administration of 0.1% albumin per day over 2-5 days.

(Visit 3) Outpatient treatment 2: IVIG 1 gram/kg over 1 day (to be administered 21±3 days after completion of initial treatment).

Placebo would include administration of 0.1% albumin per day over 1 day.

Selection of Placebo: The inclusion of placebo is critically important in a pilot study of this type in order to understand the potential treatment effects of IVIG on disease. Low dose albumin has been selected as the choice of placebo based on standard dosing from several other clinical trials of IVIG in different forms of neuropathy.

OBJECTIVES (Succinctly describe the major objectives for the overall proposed project)

To develop a therapeutic intervention for treatment induced neuropathy in diabetes. The primary endpoint will be to improve the pain associated with TIND, as well as improve nerve fiber structure (measured by biopsy analysis of IENFD) and by improvement in nerve fiber function.

Finally, we will improve our understanding of the potential mechanisms underlying this disorder, and define a potential plasma biomarker (elevated cytokines and inflammatory markers) that could identify patients that would respond to the treatment.

Primary endpoint:

The change in neuropathic pain severity and distribution between treatment and placebo groups between visit 1 and visit 2.

We expect that individuals with TIND treated with IVIG will have a >50% reduction in neuropathic pain and >30% reduction in the distribution of neuropathic pain 6 weeks after treatment. We expect that placebo that will have <20% reduction in neuropathic pain and no change in the distribution of neuropathic pain 6 weeks after treatment.

Secondary Outcomes:

The difference in quantified neurologic examination scores, biopsy scores and autonomic function between treatment and placebo groups at 6 weeks and 12 weeks.

We expect that individuals with TIND treated with IVIG will have improvements in quantified neurologic examination scores, autonomic function testing and nerve fiber density at follow up visits 4 and 5 compared to their initial visit. We expect that placebo treated individuals will have either no change or worsening of quantified neurologic examination scores, autonomic function testing and nerve fiber density at follow up visits 4 and 5 compared to their initial visit.

Exploratory Outcomes:

Exploratory outcome measures will include the effects of cytokine on neuropathic pain, small fiber neuropathy and autonomic neuropathy (heart rate variability).

Statistical Analysis Plan

Power calculations:

This pilot study is being conducted in order to obtain adequate preliminary data for a larger clinical trial, but is powered to answer the primary endpoint analysis. Secondary endpoints and exploratory endpoints are not included in the power analysis

Group	Change in pain score	Change in IENFD
Placebo	2+/-2	0.5+/-1
IVIG	5+/-3	3+/-1.9

Number of pairs needed for 80% power to detect change.	10	7
---	-----------	----------

Change in pain score calculation: We are planning a study of a continuous response variable from matched pairs of study subjects. Prior data indicate that the difference in the pain response of matched pairs is normally distributed with standard deviation 3. If the true difference in the mean response of matched pairs is 3, we will need to study 10 pairs of subjects to be able to reject the null hypothesis that this response difference is zero with probability (power) 0.8. The Type I error probability associated with this test of this null hypothesis is 0.05.

Change in IENFD score calculation: We are planning a study of a continuous response variable from matched pairs of study subjects. Prior data indicate that the difference in the response of matched pairs is normally distributed with standard deviation 1.9. If the true difference in the mean response of matched pairs is 2.5, we will need to study 7 pairs of subjects to be able to reject the null hypothesis that this response difference is zero with probability (power) 0.8. The Type I error probability associated with this test of this null hypothesis is 0.05.

Based on our preliminary data from the 4 subjects treated with IVIG, and the 104 untreated subjects with TIND, and the power analysis listed in Table 3, we calculate that 10 subjects in each of the treatment and placebo treated arms will provide >80% power with a 2 sided alpha of 0.05 to detect a difference between placebo and active treatment groups.

A total of 20 subjects will be included in this study:

- 1) IVIG treatment: Individuals with poorly controlled diabetes that have a sudden improvement in their HbA1C and the development of neuropathy (*meeting criteria for treatment induced neuropathy*). Subject number =10
- 2) Placebo Treatment: Individuals with poorly controlled diabetes that have a sudden improvement in their HbA1C and the development of neuropathy (*meeting criteria for treatment induced neuropathy*). Subject number =10.

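### Pain is scored only at Visits 1 and 4; a pain assessment before the first infusion at Visit 2, named as the baseline, would take up to 28 untreated days out of the primary change score at little cost

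*Combined protocol and SAP*

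**What the plan says.** **Pain assessments.** The Screening Visit (Visit 1) list reads "Undergo a general physical examination, Pain VAS scores, pain questionnaires and SF-36". The Visit 4 list reads "Undergo a general physical examination. Pain VAS scores, pain questionnaires and SF-36". No other visit lists a pain score.

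**Infusion visits.** Under Outpatient treatment 1 (Visit 2) and Outpatient treatment 2 (Visit 3), the only patient-reported item is the "SF-36 questionnaire". The SF-36 does not appear under Primary endpoint, Secondary Outcomes or Exploratory Outcomes.

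**Timing.** Treatment 1 is "IVIG 2 grams/kg over 2-5 days", "to be administered within 28 days of screening visit". Treatment 2 is "to be administered 21±3 days after completion of initial treatment". Visit 4 is described as "Follow up evaluation at BIDMC 28 +/- 3 days after 2nd IVIG treatment".

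**Primary endpoint.** It is the change in severity and distribution of neuropathic pain "between treatment and placebo groups between visit 1 and visit 2". The same section then predicts, six weeks after treatment, a fall in pain of more than 50% on IVIG and less than 20% on placebo. It also predicts a fall of more than 30% in pain distribution on IVIG and no change on placebo.

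**The concern.** Visit 1 to Visit 4 is the only change in pain that the schedule can produce. Its baseline is one screening assessment that may precede the first infusion by up to 28 days, so any movement in pain over those days is counted in the change score although no treatment has been given.

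Such movement is plausible. Eligibility requires pain that began within 8 weeks of a rapid HbA1C change, and the power table assumes that pain on placebo changes by 2 points. Two things are at stake:

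- **Precision of the comparison of arms.** There are only 10 patients per arm, and the gap varies from patient to patient.
- **Meaning of the within-arm reductions.** The protocol predicts these as percentages, and they would inform the larger trial.

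In addition, a patient who misses Visit 4 has no pain score after treatment at all.

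**Working it through.** **1. The plan's own figure.** For a paired t-test with difference 3, SD 3 and two-sided alpha 0.05, the noncentral t gives n = 9.94, rounded up to 10 pairs, with power 0.803. The stated 10 pairs reproduces. The trial has two independent arms, however, so the power figures below use a two-sample test. That mismatch is a separate point.

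**2. Visit windows** (from the visit schedule, counting from the first infusion day)

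- First to last day of a 2-5 day course: 1 to 4 days.
- Completion of treatment 1 to treatment 2 (21 ± 3): 18 to 24 days.
- Treatment 2 to Visit 4 (28 ± 3): 25 to 31 days.
- First infusion to Visit 4: 1+18+25 = 44 to 4+24+31 = 59 days.
- Visit 1 to Visit 4: 0+44 = 44 to 28+59 = 87 days.
- With the full 28-day gap: 28+44 = 72 to 28+59 = 87 days. The untreated share is 28/87 = 32% to 28/72 = 39%.
- With a 14-day gap: 14/73 = 19% to 14/58 = 24%.

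The opening protocol text gives 2-4 days for the first course and the visit schedule gives 2-5; these must be reconciled. With 2-4 days the upper limits become 58 and 86. If the whole course has to finish within 28 days of screening, the baseline is at most 24 to 27 days old at first infusion. The wording does not settle this.

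**3. Size of drift, as an illustration.** Assume that the plan's placebo change of 2 points accrues evenly over the window. With the full gap, 2 × 28/87 = 0.64 to 2 × 28/72 = 0.78 points would fall before any infusion.

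**4. Power, as an illustration.** The table's change-score SDs are 2 (placebo) and 3 (IVIG), so the pooled variance is (4+9)/2 = 6.5 and the SD is 2.55. The difference is 3 with 10 per arm. For variance V, the noncentrality is 3/√(2V/10) on 18 degrees of freedom. An unadjusted change score (V = 6.5) gives power 0.70.

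The assumptions, none of which is in the documents, are equal variances at each visit, a correlation r of 0.5-0.6 between either baseline and Visit 4, and a correlation ρ of 0.6-0.8 between the two baselines. Then:

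- Single-visit variance: σ² = 6.5/[2(1−r)], which is 6.5 for r = 0.5 and 8.125 for r = 0.6.
- Adjusting for Visit 1 only: V = σ²(1−r²).
- Adjusting for Visits 1 and 2: V = σ²[1−2r²/(1+ρ)].

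| r | ρ | V, Visit 1 only | Power | V, both | Power | Gain (points) |
|---|---|---|---|---|---|---|
| 0.5 | 0.6 | 4.875 | 0.819 | 4.469 | 0.851 | 3.2 |
| 0.5 | 0.8 | 4.875 | 0.819 | 4.694 | 0.833 | 1.4 |
| 0.6 | 0.6 | 5.200 | 0.794 | 4.469 | 0.851 | 5.6 |
| 0.6 | 0.8 | 5.200 | 0.794 | 4.875 | 0.819 | 2.5 |

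Spending one degree of freedom per covariate (17 and 16) lowers each power by less than one point.

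These formulas give Visits 1 and 2 the same correlation with Visit 4. The gain shown therefore comes from having two readings, not from having a fresher one. Any benefit of freshness would be extra, and the documents do not allow it to be sized.

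**The case against.** **The arms share the gap.** A reader might infer that an old baseline biases the estimated treatment effect. The documents do not support that. Patients are randomised equally, the gap precedes treatment in both arms, and the endpoint compares the arms, so expected drift cancels. What remains is added noise, chance imbalance with 10 per arm, and distortion of the within-arm percentages. This objection stands and limits the point.

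**The gain in power may be small.** A reader might expect a fresh baseline to bring a large gain. That would need an assumed jump in correlation for which the documents give no basis. On the assumptions above, most of the improvement over the 70% for an unadjusted change score comes from adjusting for the Visit 1 score already collected. This also stands. In addition, 28 days is a maximum, not a typical delay.

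**Simpler remedies fall short.** Averaging Visits 1 and 2 looks attractive, but it leaves half the baseline weight on the old score and so keeps half of any drift. A Visit 3 score is taken after the first course, so it cannot shorten the untreated gap, nor is it the Visit 4 outcome.

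**The endpoint wording is a separate fault.** Naming Visit 2 in the primary endpoint is an error of definition, and it does not by itself make the gap more harmful. It does have to be corrected once the baseline is redefined.

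**Conclusion.** The point holds as a cheap improvement, not as a flaw that invalidates the comparison. From the schedule alone, the pain baseline can be up to 28 days old at first infusion, and up to 32-39% of the measured interval can then be untreated time. A pre-infusion Visit 2 baseline reduces the window from 44-87 days to 44-59.

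The cost of leaving the design as it is consists of noise in the between-arm comparison and distorted within-arm reductions. It is not systematic bias in the treatment effect. The gain of roughly 1 to 6 points of power rests wholly on assumed correlations and equal variances, and on a baseline-adjusted analysis that the plan does not specify. The 0.64-0.78 point drift rests on an assumption of even accrual.

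**What to change.** 1. At Visit 2, before the first infusion, collect pain severity and pain distribution with the Visit 1 instruments. A VAS alone is not enough, because distribution is also part of the primary endpoint.
2. Name that assessment as the baseline for the primary change to Visit 4. The Visit 1 score may be kept as an additional covariate.
3. Rewrite the primary endpoint so that its visits match the schedule. As worded ("between treatment and placebo groups between visit 1 and visit 2"), it ends at the first infusion visit, where no pain score is planned.
4. Optionally, collect the same scores before the infusion at Visit 3. Use them only as an intermediate time point in a repeated-measures model that estimates the Visit 4 difference, never carried forward in place of a missing Visit 4.

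**Cost.** A short pain assessment at one or two visits where patients already attend and complete the SF-36, plus a sentence defining baseline. No extra visit, staff or invasive procedure is needed.

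### The primary endpoint is defined in two different ways, its headed version ends at a visit with no pain score, and the claimed power above 80% is a matched-pairs figure that becomes about 70% for the randomized comparison

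*Combined protocol and SAP*

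**What the plan says.** **Endpoint.** OBJECTIVES states: "The primary endpoint will be to improve the pain associated with TIND, as well as improve nerve fiber structure", the structure being measured by IENFD, and adds improved nerve fiber function. Under the separate heading Primary endpoint, the text is: "The change in neuropathic pain severity and distribution between treatment and placebo groups between visit 1 and visit 2". The expectation that follows includes ">30% reduction in the distribution of neuropathic pain 6 weeks after treatment".

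**Secondary.** Secondary Outcomes lists "The difference in quantified neurologic examination scores, biopsy scores and autonomic function between treatment and placebo groups at 6 weeks and 12 weeks" and expects changes in examination scores, autonomic testing and "nerve fiber density at follow up visits 4 and 5 compared to their initial visit".

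**Schedule.** The Screening Visit (Visit 1) and Visit 4 both list "Pain VAS scores, pain questionnaires and SF-36". Visit 2 is the first infusion course and Visit 3 the second; each lists only an SF-36. Visit 4 is a "Follow up evaluation at BIDMC 28 +/- 3 days after 2nd IVIG treatment". It is the last visit scheduled.

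**Design and power.** "Subjects will be randomized equally to treatment or placebo", with 20 subjects in total. Power calculations says that the pilot is powered for its primary endpoint and that secondary endpoints are left out. It then gives two matched-pairs calculations: pain (difference 3, SD 3, 10 pairs) and IENFD (difference 2.5, SD 1.9, 7 pairs). It concludes that 10 subjects per arm give more than 80% power at two-sided 0.05.

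**The concern.** The two statements of the primary endpoint share pain but differ on everything else. IENFD is primary in one, secondary in the list, and powered in a section that says it powers no secondary endpoint. Pain distribution is part of the headed primary endpoint but has no power input and no named instrument. No rule says how several components would combine into a result.

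The visit matters more. Followed literally, the headed endpoint compares screening with the first infusion visit. No pain score is listed there, and any value obtained would come before the treatment course is complete.

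The stated purpose of this pilot is to estimate the size of the effect so that a larger trial can be powered. That estimate needs one measure at one visit. The claim of more than 80% power also sets expectations for what 20 subjects can show, and it comes from a design that this trial does not have.

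**Working it through.** **1. Visits side by side**

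| Visit | What happens | Pain VAS and questionnaires listed? |
|---|---|---|
| 1 | Screening | Yes |
| 2 | First infusion course | No (SF-36 only) |
| 3 | Second infusion | No (SF-36 only) |
| 4 | Follow-up | Yes |
| 5 | Named in Secondary Outcomes, not scheduled | – |

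The only change in pain score that the schedule supports is visit 1 to visit 4.

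**2. Timing.** Visit 3 is 21 ± 3 days after completing the first course; visit 4 is 28 ± 3 days after the second treatment.
- From completion of the first course: (21 − 3) + (28 − 3) = 43 to (21 + 3) + (28 + 3) = 55 days. Six weeks is 42 days, one day before the window.
- From the second treatment: 25 to 31 days. Day 42 is 11 days after the window.
- Twelve weeks is 84 days, which is 29 days after day 55. No anchor for 12 weeks is stated, but whatever it is, two follow-up time points need two follow-up visits and only visit 4 is scheduled.

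**3. Reproducing the plan's power figures.** Paired t-test, two-sided 0.05, noncentrality = (difference / SD of paired difference) × √n.
- Pain: (3/3) × √10 = 3.16 on 9 df, power 80.3%. Solving for 80% gives n = 9.94, so 10 pairs.
- IENFD: (2.5/1.9) × √7 = 3.48 on 6 df, power 82.5%. Solving gives n = 6.70, so 7 pairs.

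Both stated figures reproduce exactly. The arithmetic is right for matched pairs.

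**4. The comparison that the design supports.** Subjects are randomized to two arms and no matching is described, so the comparison is an unpaired two-sample t-test on 18 df. The inputs are from the table under Power calculations.
- Pain: difference 5 − 2 = 3; pooled SD √((2² + 3²)/2) = 2.55. Noncentrality 3 / (2.55 × √(2/10)) = 2.63, **power 70.2%** (69% with Welch's test).
- IENFD: difference 3 − 0.5 = 2.5; pooled SD √((1² + 1.9²)/2) = 1.52. Power 93.6%.
- Precision for pain: 95% CI half-width 2.101 × 2.55 × √(2/10) = 2.40 points.

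**5. What the endpoint conflict adds.** If pain and IENFD both had to succeed:
- unpaired, table SDs: 0.702 × 0.936 = 0.656 if independent, rising to about 0.70 with strong correlation, against 0.702 for pain alone;
- on the plan's paired inputs with 10 pairs: 0.803 × 0.958 = 0.77 if independent and at most 0.803, against 0.803 for pain alone.

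The cost is 0 to about 5 points. Nothing can be computed for distribution or nerve fiber function, because the plan gives no effect or SD for them.

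**The case against.** The best defence is that the intention can be recovered. OBJECTIVES describes the overall project, so its sentence can be read as aims, and the separately headed endpoint is more specific. The expectation of an effect six weeks after treatment rules out the first infusion visit, so visit 2 looks like a slip for visit 4. Pain is collected at both visits that matter, so no data would be lost. Pain sets the sample size, since IENFD needs fewer pairs. On one count the six-week mismatch is a single day. All of this stands and limits the weight of the point. It does not remove the need for a correction: even with visit 4 substituted, the plan does not settle severity versus distribution, the status of IENFD, or how components combine.

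It is also fair that the drop from 80% to 70% comes from pairing and not from the endpoint wording. Naming one endpoint does not restore it. It belongs here because the plan attaches the claim to the primary endpoint.

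Stronger readings that a reader might infer, and why the documents do not support them:
- **Power is only 56% and 17 per arm are needed.** This puts SD 3 in both arms. The plan uses 3 for the paired difference and gives 2 for placebo in its table. It is a pessimistic sensitivity case, no more.
- **Type I error rises to 9.75% (two measures) or 14.3% (three).** This requires that any one significant, independent component count as success. No such rule is stated, and the wording leans towards requiring all, under which there is no inflation.
- **Requiring severity and distribution together sharply cuts power.** Any figure would rest on an assumed power for distribution, for which the plan has no input.
- **The sample must grow.** A pilot can keep 10 per arm if it states its power and precision correctly.

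**Conclusion.** The point holds. The primary endpoint is stated inconsistently. The headed version ends at a visit with no listed pain score, before the treatment course is complete. The 6-week, 12-week and visit 5 references do not fit the schedule. The power section contradicts itself on IENFD.

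For pain severity with 10 per arm, power is about 70%, not more than 80%. If IENFD were also required it would be about 66% to 70%. These figures assume the table's differences and per-arm SDs, normal data, an unpaired t-test at two-sided 0.05, and no dropout.

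The effect of the endpoint ambiguity on power is small. Its real cost is that the quantity the pilot exists to estimate is not uniquely defined. This should be corrected, and wording is enough.

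**What to change.** 1. In both OBJECTIVES and Primary endpoint, state one primary endpoint: the between-arm difference in change in pain severity score from visit 1 to visit 4, tested at two-sided 0.05, with the instrument named. Pain VAS is collected at both visits. Name the test as an unpaired comparison. Use one scale throughout, since the expectations are in percent and the power table is in points.
2. List pain distribution, IENFD, UENS and heart rate variability as secondary in both places. If distribution is to stay confirmatory, test it second in a fixed order and name its measure.
3. Replace the 6-week references with visit 4 and its window. Reconcile 12 weeks and visit 5 with the schedule, or delete them.
4. Label the IENFD calculation as supporting a secondary endpoint, and correct the sentence that excludes secondary endpoints from the power analysis.
5. Keep 10 per arm and withdraw the claim of more than 80%. State about 70% power for pain (unpaired, table SDs) and an expected 95% CI half-width of about 2.4 points.

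**Cost.** Wording only: no extra subjects or procedures. Distribution and IENFD can no longer be claimed as primary results, the stated power is less favourable, and deleting visit 5 gives up the intended 12-week result.

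### The primary endpoint ends at visit 2, the first infusion course, where no pain score is scheduled; pain is scored only at visits 1 and 4

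*Combined protocol and SAP*

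**What the plan says.** The Primary endpoint section reads "The change in neuropathic pain severity and distribution between treatment and placebo groups between visit 1 and visit 2". The two sentences after it give the expected results in each arm and place them six weeks out; for IVIG, for example, they expect a "reduction in the distribution of neuropathic pain 6 weeks after treatment".

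The visit schedule says the following:

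- **Visit 1 (screening):** "Undergo a general physical examination, Pain VAS scores, pain questionnaires and SF-36".
- **Visit 2:** "Visit 2) Outpatient treatment 1: IVIG 2 grams/kg over 2-5 days (to be administered within 28 days of screening visit". The one assessment listed is the "SF-36 questionnaire".
- **Visit 3:** the second infusion, "to be administered 21±3 days after completion of initial treatment", again with the SF-36 alone.
- **Visit 4:** "Visit 4: Follow up evaluation at BIDMC 28 +/- 3 days after 2nd IVIG treatment", where subjects "Undergo a general physical examination. Pain VAS scores, pain questionnaires and SF-36".

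No later visit is described. The Secondary Outcomes section nevertheless compares the arms at 6 and 12 weeks and twice refers to follow-up visits 4 and 5. The SAP's Power calculations section says the study is powered for the primary endpoint but gives no time point for the pain changes it assumes (2+/-2 on placebo, 5+/-3 on IVIG).

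**The concern.** A change score needs a measurement at both ends. The endpoint sentence ends at a visit where the schedule lists no pain measurement and where treatment is only being started. The SF-36 does not fill the gap: at visits 1 and 4 the protocol lists it separately from the pain VAS and pain questionnaires, so the protocol does not treat it as the pain score.

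What is at stake is a primary definition that does not match the data to be collected. An analyst who follows it literally has nothing to analyse. One who uses visit 4 instead departs from the written primary endpoint of a double-blind, placebo-controlled trial whose effect estimate is meant to size a larger trial. The scope for choosing a visit after seeing the data is small, because visit 4 is the only described post-treatment visit with pain scores.

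**Working it through.** **The plan's own figure.** The number tied to the primary endpoint is 10 pairs (difference 3, SD of the paired difference 3, two-sided alpha 0.05, power 0.80). A paired t-test with the noncentral t distribution gives power 0.748 at 9 pairs and 0.803 at 10, so the figure reproduces. It carries no visit or week, so it cannot show which visit was meant, and nothing below changes it.

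**Where pain is measured.**

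| Visit | Role | Pain VAS and pain questionnaires | SF-36 |
|---|---|---|---|
| 1 | Screening | Yes | Yes |
| 2 | First infusion course | Not listed | Yes |
| 3 | Second infusion | Not listed | Yes |
| 4 | Follow-up | Yes | Yes |

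Pain is scheduled at 2 of 4 visits, and at visit 2 for 0 of 20 subjects.

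**How far the written endpoint falls short of the follow-up score.** Inputs are the visit 3 and visit 4 windows in the visit schedule.

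- Visit 3 after completion of course 1: 21 ± 3 = 18 to 24 days.
- Visit 4 after the second infusion: 28 ± 3 = 25 to 31 days.
- Visit 4 after completion of course 1: earliest 18 + 25 = 43, nominal 21 + 28 = 49, latest 24 + 31 = 55 days.

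Counted from completion of course 1, the endpoint as written therefore ends 18 to 24 days before the second infusion and 43 to 55 days before the follow-up pain score. These sums do not use the length of the first course, which the opening paragraph gives as 2-4 days and the visit schedule as 2-5 days; those two statements also need to be reconciled.

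**Lesser item (a): six weeks (42 days) against visit 4.** The expectation sentences do not say which treatment the six weeks run from.

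- From completion of course 1, the nearest edge is 43 − 42 = 1 day off. Screening and the first infusion day are no later than that, so visit 4 is at least 43 days after them too.
- From the second infusion, the nearest edge is 42 − 31 = 11 days off.

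**Lesser item (b): twelve weeks (84 days) and visit 5.**

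- From completion of course 1: 84 − 55 = 29 days past the latest visit 4.
- From the second infusion: 84 − 31 = 53 days past it.

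The described schedule therefore contains no 12-week assessment.

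**Which visit was meant.** The six-week expectation rules out visit 2. The Secondary Outcomes section names 6 and 12 weeks and then visits 4 and 5. Matching them in order puts visit 4 at six weeks, which is where the primary effect is expected. Visit 4 is also the only described post-treatment visit with pain scores.

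**The case against.** The strongest reply is that this is a typing slip in a 20-subject pilot. The very next sentences speak of six weeks after treatment, the pain data are already scheduled, and any sensible reader would use visit 4. Most of that is right, and the six-week sentences do show intent. They do not name a visit, however, and they state expectations; they do not define the endpoint. A probable cause does not make the definition usable.

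A second reply pulls the other way: because visit 5 is mentioned without procedures, pain scoring there can be neither confirmed nor excluded, so visit 4 is not proven. It is an inference, and the sponsor should confirm it. But the pairing of weeks and visits in the Secondary Outcomes section makes visit 4 the indicated one.

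Third, the one-day gap in item (a) is trivial, and it depends on the visit schedule's anchor. The opening paragraph only puts the second treatment three weeks later, give or take three days. If that ran from the start of a 2-4 day course on consecutive days, the earliest visit 4 would be 40 to 42 days after completion, and day 42 could fall inside the window. This stands, and the conclusion does not rest on item (a).

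Finally, changing the visit number does not settle everything. No instrument is named for pain distribution, and the Objectives section also lists nerve fibre structure and function under the primary endpoint. Both remain open after this edit.

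**Conclusion.** The contradiction is real and must be fixed. As written, the primary endpoint has no scheduled pain score at its end point for any of the 20 subjects and stops 43 to 55 days (nominally 49), counted from completion of course 1, before the only scheduled follow-up pain score. Confidence is high, because this follows directly from the schedule.

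Reading visit 4 as the intended visit is an inference, though a well-supported one. Whether the pain changes assumed in the power calculation correspond to visit 4 cannot be determined, because no time point is given for them. Items (a) and (b) are smaller inconsistencies to clear up in the same edit and do not drive the severity.

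**What to change.** 1. Replace the endpoint sentence with: *The between-arm difference (IVIG versus placebo) in the change in neuropathic pain severity and distribution from visit 1 to visit 4.*
2. Replace the six-week references with visit 4 (28 ± 3 days after the second study infusion) in three places: both primary expectation sentences and the secondary outcomes sentence.
3. In the Secondary Outcomes section, delete the 12-week time point (one place) and change visits 4 and 5 to visit 4 (two places). If the sponsor does intend a 12-week visit 5, keep these references and add the visit to the schedule with a window and a list of procedures.

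The sponsor should confirm visit 4 before the text is changed.

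**Cost:** text edits in 1 + 2 + 1 + 2 = 6 sentences, with no new visit, no new pain VAS or questionnaire assessment, and no change to the sample size. Keeping visit 5 would add one visit per subject, 20 × 1 = 20 visits. Moving visit 4 so that its window includes day 42 would be a change of schedule and is not part of this fix. The measure of pain distribution still has to be named before that half of the endpoint is shown to have data.
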